5.4. Selected secondary endpoints

The following secondary endpoints are of particular clinical interest and will undergo further

sensitivity analyses like subgroup analyses.

- Change from baseline FEV₁ to peak FEV₁ (over 3 hours) at Week 4
- Change from baseline FEV₁ to morning trough FEV₁ at Week 4
- Change from baseline FEV₁ to average FEV₁ (over 12 hours) at Week 4

5.5. Efficacy Endpoints details

5.5.1. Pulmonary Function Tests

Baseline FEV₁ is defined as the FEV₁ pre-dose assessment (-15 minutes) collected at Visit 2.

Peak FEV₁ (over 3 (12) hours) is defined as the maximum post-dose value among the values collected up to 3 (12) hours.

Morning trough FEV₁ is defined as the last pre-dose value at the visit under analysis

Average FEV₁ (over 3 (12) hours) is defined as the Area under the curve AUC₀₋₃ (AUC₀₋₁₂) of the FEV₁ values collected during the visit under analysis, divided by the length of the time (in hours) interval of interest. The AUC is calculated using the trapezoidal rule.

Parameters will be calculated over 3 hours (at Day 1 and Week 1 to 4) and over 12 hours (Day 1 and Week 4).

If patient miss hour 2 and 3 then the AUC 0-3 is set to missing. If patient miss hour 8 and 12 then AUC 0-12 is set to missing.

Censoring of value after rescue medications: before derivation of endpoints, within each visit, the spirometry data collected after the use of rescue medications (either Albuterol / Salbutamol or Ipratropium as collected on the CRF) will be censored (i.e.: considered as missing)

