5.4.2.1 Nebulized RPL554 and Placebo

The RPL554 study drug will be administered by inhalation of an aerosol generated by a reusable PARI LC Sprint[®] jet nebulizer attached to a compressor (PARI TurboBOY[®] SX in the EU, or PARI Vios[®] PRO in the U.S.). Patients will receive a compressor at the randomization visit, and a LC Sprint nebulizer at each visit.

[REDACTED]

The end time of nebulization (sputtering) of the study medication will be considered Time 0 for the purposes of scheduling all post-dose study procedures. Nebulization time should be approximately 5 minutes and may not exceed 10 minutes.

For the in-clinic nebulizations, the following must be recorded in the eCRF:

- Start and end times of nebulization (times will be rounded down to the nearest minute)
- The volume of residual product at the end of nebulization

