9.2.2.4 Extent of Exposure and Treatment Compliance

Compliance will be calculated based on two parameters – the number of used and unused vials returned and the dosing recorded in the e-diary. Total exposure will be based on the compliance with dose and the dose group the subject was randomized into. For in-clinic dosing, the RPL554 exposure will be calculated based on the nominal dose.

9.2.2.5 *Efficacy*

For FEV₁ the average effect (E_{av}) will be calculated as the AUC divided by the length of the time interval of interest. In addition, the peak effect on FEV₁ during these time intervals will be computed as the maximum value (E_{max}) and the trough FEV₁ as the value at 12 hours prior to next dose administration. Parameters will be calculated both over 3 hours (Visits 2 to 6) and over 12 hours (Visits 2 and 6). For withdrawn patients, values from last visit performed will be imputed. The peak FEV₁ is the highest value in the 3 hours after dosing.

Computed pharmacodynamic parameters for FEV_1 will be compared between the five study medications using (additive) analysis of covariance (ANCOVA) models with fixed factors for treatment and country(/center) and using the baseline FEV_1 (pre-dose at Visit 2) as a covariate. Parameters will be analyzed both after single-dose (Visit 2), at end-of-study (Visit 6/last visit) or as the average over Visits 3 to 6. The total score for the EXACT-PRO will be summarized for each day and the average weekly scores during the treatment period as well as the average over the full treatment period will be calculated. The average over last 7 days of the run-in period will be used as baseline.

Verona Pharma plc CONFIDENTIAL Page 55 of 67

Sites will be consolidated to the country level, which will be used as a fixed factor in all analyses in order to help reduce the variability in data. At least for the primary variable, secondary analyses investigating impact of country will be performed. Depending on differences in variance structure between countries, either separate models will be applied by country to estimate the treatment effect within each stratum or a full model including a treatment by country interaction term will be used to provide these estimates. No formal treatment by country test is planned.

The average daily use of rescue medication during the full treatment period and during each week will be calculated. The average over last 7 days of the run-in period will be used as baseline.

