Abbreviations: BDI=Baseline Dyspnea Index; ECG=electrocardiogram; ICS=inhaled corticosteroids; MRC=Medical Research Council; QTcF=QT interval corrected using Fridericia's formula; PGAC=Patient Global Assessment of Change; PK=pharmacokinetics; SGRQ-C=St George's Respiratory Questionnaire-COPD specific; TDI=Transition Dyspnea Index

(a) Informed Consent may be obtained prior to screening visit
(b) Serum pregnancy test at Visit 1; urine pregnancy test at Visits 2-6
(c) At Visit 2, study medication is to be administered at the study clinic twice; first, just after randomization and again 12 hours later once all assessments are complete
(d) Spirometry at Visits 2 and 6 is performed 15 minutes pre-dose, followed by 30 minutes and 1, 2, 3, 4, 6, 8 and 12 hours post-dose
(e) Spirometry at Visits 3, 4, and 5 are performed 15 minutes pre-dose, followed by 30 minutes and 1, 2, and 3 hours post-dose
(f) Vital signs at Visits 2 and 6 are measured pre-dose and 30 minutes, 1, 2, 4, 6, 8, and 12 hours post-dose
(g) Vital signs at Visits 3, 4, and 5 are measured pre-dose and 30 minutes, 1, 2 and 3 hours post-dose
(h) ECG at Visits 2 through 6 is performed pre-dose and 2 hours post-dose
(i) BDI administered at Visit 2, TDI administered at Visits 4 and 6
(j) A second canister of albuterol/salbutamol may be dispensed during the study if necessary
(k) Holter is to be removed 24 hours (± 1 hour) after placement

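### SAP 5.5.1 keeps an average FEV1 that lacks only its last reading but gives no rule for the uncovered tail; applied as written, that average is about one third too low

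*SAP*

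**What the plan says.** SAP 5.5.1 defines average FEV1 as the trapezoidal AUC of the FEV1 values collected at the visit, "divided by the length of the time (in hours) interval of interest". The intervals are fixed: "Parameters will be calculated over 3 hours (at Day 1 and Week 1 to 4) and over 12 hours". Protocol 9.2.2.5 has the same definition; the average effect "will be calculated as the AUC divided by the length of the time interval of interest".

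There are two completeness rules: "If patient miss hour 2 and 3 then the AUC 0-3 is set to missing" and "If patient miss hour 8 and 12 then AUC 0-12 is set to missing". Neither mentions a profile in which only the final reading is absent.

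The same section treats as missing "the spirometry data collected after the use of rescue medications" within a visit. SAP 3.8.1 names the MMRM as the way to deal with missing efficacy data, allows LOCF only as a sensitivity analysis of the primary endpoint, and excludes any other imputation. Protocol 9.2.3 gives visit-level LOCF and a one-reading rule for the peak, and leaves further detail to the SAP.

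On timing, SAP Appendix 1 states "Spirometry at Visits 2 and 6 is performed 15 minutes pre-dose, followed by 30 minutes", and then readings at 1, 2, 3, 4, 6, 8 and 12 hours. Visits 3 to 5 stop at 3 hours. Under Protocol 5.4.2.1 the end of nebulization "will be considered Time 0 for the purposes of scheduling all post-dose study procedures", but no reading is scheduled at that moment and SAP 5.5.1 does not say which value stands at time 0.

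**The concern.** The completeness rule, the divisor and the ban on other imputation do not fit together. The first keeps a profile that ends at 2 h or 8 h, the second divides by 3 or 12, and the third leaves nothing to fill the gap. The numerator and divisor then cover different lengths of time. Because baseline is a single pre-dose FEV1, the whole shortfall passes into the change from baseline.

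The plan's own rescue censoring can produce this pattern. Rescue between 2 and 3 h removes only the last reading of the 3-hour profile, and rescue between 8 and 12 h removes only the last reading of the 12-hour profile. Earlier rescue normally removes both late readings, and the existing rule covers that case. If rescue use differs between arms, the error need not cancel.

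The endpoints exposed are average FEV1 over 3 hours (Day 1, Weeks 1 to 4) and over 12 hours (Day 1, Week 4). SAP 5.4 singles out the Week 4 12-hour average as of particular clinical interest, and SAP 5.6.6 also analyses it in subgroups, where one affected patient weighs more.

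**Working it through.** **The plan's own figure.** The plan gives none for this point. Its only design figure concerns peak FEV1 and reproduces: (1.960 + 0.842) × 250 × √(2/80) = 110.7 mL, against the stated 111 mL. It does not bear on the average.

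**Inputs.** Reading times, intervals and completeness rules are from SAP 5.5.1 and Appendix 1. FEV1 levels, profile shapes and rates of missing last readings are assumptions, because the documents give none. The pre-dose reading is placed at time 0.

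**Flat profile at level b, last reading missing.**
- 0-12 h: AUC to 8 h divided by 12 = 8b/12 = 0.667b.
- 0-3 h: AUC to 2 h divided by 3 = 2b/3 = 0.667b.
- Error = -b/3 (33.3% low): -333, -433 and -500 mL at b = 1.0, 1.3 and 1.5 L.

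**Declining active profile.** FEV1 rises linearly from b to b + peak at 1 h, then falls linearly to b + res at 12 h. Example: b = 1.3, peak = 0.2, res = 0 L.

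| | 0-12 h | 0-3 h |
|---|---|---|
| Complete average | 16.800/12 = 1.400 L | 1.455 L |
| As written | 11.455/12 = 0.955 L (-445 mL) | 2.891/3 = 0.964 L (-491 mL) |
| Divide by covered time | 11.455/8 = 1.432 L (+32 mL) | 2.891/2 = 1.445 L (-9 mL) |
| Carry last reading to the end | (11.455 + 4 × 1.373)/12 = 1.412 L (+12 mL) | (2.891 + 1.482)/3 = 1.458 L (+3 mL) |

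Over b = 1.0, 1.3, 1.5 L and (peak, res) = (0.1, 0), (0.2, 0), (0.2, 0.05), (0.2, 0.1), (0.3, 0) L:
- As written: -339 to -539 mL over 12 h (31% to 33% low); -362 to -586 mL over 3 h (about 34% low).
- Covered time: +14 to +48 mL over 12 h; -5 to -14 mL over 3 h.
- Carried reading: +6 to +18 mL over 12 h; +2 to +5 mL over 3 h.

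**Arm means** (simple averages, flat profile, b = 1.3 L). One affected patient lowers the mean of an 80-patient arm by 433/80 = 5.4 mL. For an assumed subgroup arm of 40 or 20 patients the shift is 10.8 or 21.7 mL.

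**Unequal rates.** Shift in active minus placebo ≈ (p_placebo - p_active) × b/3. With b = 1.3 L, an excess on placebo of 1, 3 or 5 points gives 4, 13 or 22 mL in favour of active drug. The same excess on active reverses the sign.

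**Equal rates, against a flat placebo.** Only the difference between the two errors remains. In the 12-hour example this is 445 - 433 = 12 mL times the affected fraction, or 0.6 mL at 5%. Across the five profiles it is 6 to 39 mL times the fraction over 12 h (0.3 to 2.0 mL at 5%) and 29 to 86 mL over 3 h (1.4 to 4.3 mL at 5%). The shortcut of one third of the treatment difference assumes a constant effect. Over 12 h it would give 17 to 50 mL on these profiles, which is too much, so it is not used. Noise rises modestly: with the peak FEV1 SD of 250 mL borrowed, a 5% rate gives √(250² + 0.05 × 0.95 × 433²) = 267 mL.

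**The case against.** The strongest reply is that the SAP never describes dividing an 8-hour AUC by 12. It defines an AUC over 0-12 h divided by 12 h and is simply silent when the tail is absent. Two readings avoid the error: taking the conjunction in the completeness rule to mean either reading, or dividing by the time observed. A programmer would probably question a fall of some 400 mL. This stands in part. A reader might infer that the plan instructs this division, and the text does not go that far. But neither harmless reading is written down. The either-reading interpretation would also discard profiles lacking only hour 8, which the trapezoid can bridge from 6 to 12 h. A programmer who spotted the problem would have to choose a remedy that nobody had prespecified.

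The second reply is that the pattern should be uncommon. Under Protocol 3.1 patients stay in clinic for at least 12 hours after dosing at Visit 6, and rescue during a clinic visit is discouraged. At Visit 2 the second dose is given in clinic at about 12 hours, after the assessments. This stands: the rates used above are illustrations only.

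The third reply concerns time 0. The AUC label begins at 0 and the values collected at the visit include the pre-dose reading, so using that reading is the natural interpretation. This also stands; one clarifying sentence is enough.

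**Conclusion.** The gap is real and the severity is minor. As written, an average lacking only its last reading is kept and reads about one third low: 31% to 34% with a time-0 value. That proportion follows from the visit grid (4 of 12 hours, 1 of 3 hours) and hardly depends on the profile. The millilitre figures rest on assumed FEV1 levels.

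A reader might infer that the trial's main result is at risk or that the error favours active drug. The documents support neither. The primary peak FEV1 uses no AUC, and SAP 5.6.5 treats the secondary endpoints as exploratory. The direction depends on which arm loses more last readings, and no rates are given. At equal rates the effect on the contrast is small. The risk that remains is imbalance between arms: about 22 mL for 5 points at an assumed 1.3 L, with larger shifts per affected patient in subgroups.

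**What to change.** Amend SAP 5.5.1 before unblinding so that numerator and divisor cover the same time.

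- Keep the rule for two missing late readings.
- When only the 3 h or 12 h reading is missing or censored, carry that visit's last uncensored reading to the end of the interval. Name this as an exception in SAP 3.8.1.
- State that the pre-dose reading is used at time 0.
- As a sensitivity analysis, set these averages to missing and leave them to the MMRM.
- Report by arm how many averages lack only the last reading, and how many of those follow rescue.

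Dividing by covered time is a simpler alternative, but over 12 h it reads 14 to 48 mL high on the declining active profiles and about 0 on a flat placebo, so it can favour active drug. At equal rates its 12-hour contrast bias exceeds that of the literal calculation in three of the five profiles. Carrying the reading leaves at most 18 mL per affected patient on the same profiles, so a 5-point excess of such patients on active would move the contrast by under 1 mL (0.05 × 18 = 0.9).

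The cost is a few sentences, a small change to the derivation program and one extra table. A small upward residual remains, and it could be larger where lung function was falling when rescue was taken. The set-to-missing analysis has limits too: the 12-hour average exists only at Day 1 and Week 4, so the model has one other visit to draw on, and missingness after rescue may be informative.

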5.5.2. Symptom Diary [EXACT-PRO]

Once patients provide answers to all 14 questions on the ePRO, the device produces a score for each of three subscales: breathlessness, cough/sputum and chest symptoms. In addition to the subscale scores, a total score (covering all 14 questions) and a score for the E-RS part (11 questions) together with the subscores will be obtained.

The average over the week 1, 2, 3 and 4 will be used as timepoint values, while the one over the week just prior to randomization (visit 2) will be used as baseline. If less than 4 days are available, the average over that week is set to missing.

Scoring will be performed as described in Appendix 2: EXACT-PRO and E-RS Scoring Instructions .

Note that, as the data are collected with an e-diary, there is no possibility of having missing items in the questionnaire as the system does not allow the patient to skip items.

Also note that the EXACT-PRO subscale scores are not endpoints of the study but will be summarized for eventual comparison with other published studies

5.5.3. St. George's Respiratory Questionnaire – COPD specific (SGRQ-C)

Patients will be asked to complete the SGRQ-C while they are at the study site at Visits 2

(baseline), 4 and 6. This is a 14-question, multiple-choice questionnaire that has 2 parts. Part 1 (questions 1-7) produces the symptoms score, while part 2 (questions 8-14) produces the activity and impacts scores. A total score is also produced. Each possible answer to each of the 14 questions is assigned a weight as in Appendix 3: SGRQ-C (Jones P. , 2012). The lowest possible weight is zero, the highest is 100. A single response is required to each item. With electronic collection, it is impossible that there could be multiple responses given to any one item.

The SGRQ-C is scored in 2 steps:

1. Sum the weights for all items with a positive response

The **symptoms component** score is obtained by adding the weights for items 1 through 7.

The **activity component** score is obtained by adding the weights for the positive responses to items Questions 9 and 12.

The **impacts component** score is obtained by adding the weights of items 8, 10, 11, 13 and 14 in the following way: the weights for all positive responses to items in Questions 10, 11 and 13 are summed together with the response to the single item that should have been checked/ticked in Questions 8 and 14.

2. Calculate the score

The score for each component is calculated separately by dividing the summed weights by the maximum possible weight for that component and expressing the result as a percentage.

$$Score = 100 * \frac{\textit{Summed weights from all positive items in that component}}{\textit{sum of maximum weights for all items in that component}}$$

The total score is calculated similarly

$$Score = 100 * \frac{\textit{Summed weights from all positive items in the questionnaire}}{\textit{sum of maximum weights for all items in the questionnaire}}$$

The total score is calculated by summing the weights to all the positive responses in each component.

Please note that by “positive items”, it is meant those that show the presence of symptoms, to some degree. For example, in question 1 (part 1), all answers (“most days”, “several days” and “with chest infections”) except “not at all” would be positive. Another way to identify a positive response from a negative one is that a positive response has a nonzero score, unlike a negative one. The same definition is true in part 2. With question 8 for example (“How would you describe your chest condition?”), the following responses are positive: “the most important problem I have”, “causes me a few problems”; an answer of “Causes no problem” would be deemed negative as it does not show any signs of symptoms. In question 14 (see Appendix 3: SGRQ-C), as another example, any answer except “It does not stop me doing anything I would like to do” would be considered positive.

Note that, as the data are collected with an e-diary, there is no possibility of having missing items in the questionnaire as the system does not allow the patient to skip items.

5.5.4. Medical Research Council (MRC) Breathlessness Scale

The MRC is the most commonly used, validated scale to assess dyspnea in daily living in chronic respiratory diseases (Mahler & Wells, 1988) (Hajiro, et al., 1998). During Visits 2 (baseline), 4 and 6, patients will be provided with the MRC (shown in Table 2 below) and asked on a grade of 1 to 5 how they would describe their levels of breathlessness.

Table 2: MRC Breathlessness Scale

Grade	Degree of breathlessness related to activities
1	Not troubled by breathlessness except on strenuous exercise
2	Short of breath when hurrying on the level or walking up a slight hill
3	Walks slower than most people on the level, stops after a mile or so, or stops after 15 minutes walking at own pace
4	Stops for breath after walking about 100 yds or after a few minutes on level ground
5	Too breathless to leave the house, or breathless when undressing

This scale will be summarized at the time points at which it is collected, which are the same as SGRQ-C.

5.5.5. Patient Global Assessment of Change (PGAC)

At visits 4 and 6, patients will be asked to respond to a PGAC question along the following lines: “compared with prior to the study start, how do you feel your breathing is?” Answers are expected to use a 1-5 scale, where 1=much worse to 5=much better, with 3= no change. Answers will be summarized at visits 4 and 6, when the questionnaire is administered.

5.5.6. Baseline and Transition Dyspnea Indices (BDI and TDI)

The BDI and TDI are interviewer-administered ratings of dyspnea severity. They are based on three components that evoke dyspnea in activities of daily living. The questionnaires are comprised of 24 items covering 3 domains.

The domains are the following:

- For BDI: Functional impairment, magnitude of task and magnitude of effort. Patients are asked to recall during the previous 2 weeks. Each of these components ranges from 0 to 4.

The BDI Total Score is the sum of the three domains and can take values from 0 to 12 (12 meaning no dyspnea) and is only assessed at baseline. The lower the score, the worse the dyspnea severity.

- For TDI: Change in functional impairment, change in magnitude of task, change in magnitude of effort. Each of these components ranges from -3 (major deterioration) to +3 (major improvement)

The TDI assesses the patient perception of the change in dyspnea severity from baseline. The TDI total score is the sum of the three TDI domains and can take values from -9 to 9. As with the BDI, the lower the TDI score, the more severe the dyspnea.

5.6. Efficacy Endpoint Analysis

5.6.1. General consideration on the analysis of efficacy

All efficacy analyses will be performed on the Full Analysis Set. Patients will be analyzed according to the randomized treatment. All efficacy summaries will present the five treatment groups. All data summarized will also be listed.

5.6.2. Analysis of Primary Endpoint

The primary efficacy analysis parameter is change from baseline FEV₁ to peak FEV₁ at Week 4 of treatment. The primary analysis will be based on the full analysis set.

Summary statistics for FEV₁ will be presented for baseline, week 4 and change from baseline by treatment group on patients with both assessments.

The primary analysis will use a restricted maximum likelihood (REML)–based repeated-measures approach. The change from baseline FEV₁ (at Day 1, Week 1, 2 3 and 4) will be the dependent variable. The analyses will include the fixed, categorical effects of treatment, visit, and treatment-by-visit interaction as well as the continuous, fixed covariates of baseline value. An unstructured (co)variance structure shared across treatment groups will be used to model the within-patient errors. If the model does not converge a compound symmetry (co)variance structure will be used. The Kenward-Roger approximation will be used to estimate denominator degrees of freedom and adjust standard errors. Analyses will be implemented with SAS PROC MIXED (see Appendix 4: SAS code for efficacy analysis). The primary comparison will be the contrast (difference in least squares mean [LSMEAN]) between treatments at Week 4.

